10. ALT > 750 IU/L
 - a. May resume previous dose when ALT < 500
11. Pregnancy
12. Liver transplantation
13. Signs or symptoms of TEN or SJS.
14. Breast feeding.
15. Allergic reaction of Grade 3 or Grade 4.
16. Evidence for behavior or ideation predisposing to suicide (increase in C-SSRS score of 1 from previous test score).

A Preliminary Study of the Efficacy and Safety of Carbamazepine in Severe Liver Disease Due to Alpha-1 Antitrypsin Deficiency

SCREENING AND MANAGEMENT FOR SPECIFIC ADVERSE EVENTS

Patients entering the study will have evidence of chronic liver disease from AT deficiency. At entry into the study, patients may have one or more of the following: elevated serum aminotransferase levels, jaundice, elevated total and direct bilirubin, medically treated ascites, esophageal and/or gastric and/or hemorrhoidal varices, biochemical evidence of hypersplenism with a white blood count (WBC) and platelet count (PLT) below the normal range, and a prolonged prothrombin time (PT) or International Normalized Ratio (INR). Adverse events will be assessed using the Common Terminology Criteria for Adverse Events (CTCAE) Version 4.0. Baseline laboratory values for patients entering the study will likely be above the normal range in the case of ALT, AST, total bilirubin, and INR and below the normal range for hemoglobin, WBC, platelets and neutrophils count. Therefore, changes in laboratory values after initiation of the study drug will need to be assessed within the context of the patient's baseline laboratory tests. We will not be reporting every variation in subject lab results as an adverse event. Small deltas from within normal limits to just outside the normal range are not clinically significant in the care of patients and should not be used to define AEs. The investigative team will use standards that define a minimum delta that determines when a change becomes an AE, either as a discrete value change or a percentage change. These can be used in combination with claims of clinical significance by the site investigator.

An increase of CP score to > 12 , development of Grade III-IV encephalopathy, or total bilirubin > 7 mg/dl will be considered a treatment failure and therapy will be discontinued. Therapy will not be restarted in these subjects even if there is an improvement in clinical status.

Alterations in liver function:

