CBZ and its metabolites are transferred to breast milk and can result in transient cholestatic hepatitis[45]. The estimated dose given to a breast feeding infant is 2-5 mg/kg/day. Breast feeding will not be allowed while the mother is receiving CBZ.

Adverse events

Definition

An adverse event (AEs) is any adverse change from the patient's baseline (pre-treatment) condition, including intercurrent illness which occurs during the course of the trial, after the consent form has been signed, whether the event is considered related to treatment or not.

A serious adverse event (SAE) is an untoward medical occurrence that results in any of the following: Death, or an event that is either life-threatening (risk of death at the time of the event) requires in-patient hospitalization or prolongation of existing hospitalization, or results in persistent or significant disability/incapacity or congenital abnormality or birth defect. Important medical events that do not result in one of the events listed above may be considered a serious adverse event when, based upon appropriate medical judgment, they may jeopardize the patient and may require medical or surgical intervention to prevent one of the outcomes listed above.

A SAE which is unexpected and is drug related (even remotely) will require expedited reporting to the FDA and the University of Pittsburgh IRB in accordance with respective timeline requirements. The following events are disease outcomes and will not be considered to be serious adverse events as they can occur in the usual course of patients with AT deficiency.

1. Development of hepatocellular carcinoma
2. Complications associated with chronic liver disease which include, but not limited to
 - a. Worsening ascites
 - b. Bleeding from esophageal, gastric, or hemorrhoidal varices
 - c. Worsening hypersplenism (hard to differentiate from bone marrow toxicity)
 - d. Hepatic encephalopathy
 - e. Hepatopulmonary syndrome
 - f. Portopulmonary hypertension
3. Extra-hepatic conditions related to alpha-1 antitrypsin deficiency which include, but not limited to
 - a. Chronic obstructive pulmonary disease
 - b. Hypoxia

Data collection procedures for adverse events

Patients will be interviewed regarding medical conditions, medication changes, and symptoms that have occurred at each study visit. An AE form will be completed if any adverse event is reported.

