A Preliminary Study of the Efficacy and Safety of Carbamazepine in Severe Liver Disease Due to Alpha-1 Antitrypsin Deficiency

If a study coordinator or investigator learns of any hospitalizations or other adverse events between study visits, an AE form will be completed. All AEs and SAEs from time of study entry (consent) up to the end of follow-up will be reported to the Sponsor-Investigator. A SAE form will be completed for all adverse events rated as serious. Patients will be followed for all ongoing unresolved adverse events until they are either resolved, or in the opinion of the Sponsor-Investigator or treating sub-investigator, the patient is medically stable.

The Sponsor-Investigator will assess the relationship of each adverse event to the use of study drug, based on available information, using the following as guidelines:

1. Unlikely related: No temporal association, or the cause of the event has been identified; or the drug cannot be implicated.
2. Possible related: Temporal association is present, but other etiologies are likely to be the cause; however, involvement of the drug cannot be excluded.
3. Probably related: Temporal association is present; other etiologies are possible, but unlikely.

Reporting procedures

All SAEs that are unexpected and related to study drug will be reported to the Sponsor-Investigator within 72 hours by telephone. This reporting includes serious adverse events that occur from the time the patient has signed the clinical trial consent. The Sponsor-Investigator will promptly review all SAEs and will notify the reviewing IRB and FDA within requisite time frames if an event is considered to be unexpected and possibly or definitely related to the study drug (e.g., *serious, unexpected adverse events related to the investigational drug to the agency within 15 days of the Sponsor becoming aware of such; deaths and life-threatening reactions reported to the agency within 7 days of the Sponsor's awareness*). The Sponsor-Investigator will notify all sub-investigators of unexpected SAEs related to the CBZ. Status reports on all adverse events will be generated under the direction of the Sponsor-Investigator and sent to the DSMB every month and will include the relationship of the AE to trial medication, the severity of the event and if the event is resolved or ongoing. All AEs will be reported annually to the FDA and reviewing IRB, as required

Statistical considerations

Analysis

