Adverse events. Summaries of adverse events (number adverse events, number and percentage of subjects with adverse events, rates per person-months) will be provided. Events will be summarized based on the date of onset for the event. A treatment emergent adverse event will be defined as an adverse event that begins on or after the date of first dose of study drug. Events that occur prior to the first dose of study medication or after the last dose of study medication will be summarized separately.

Summaries of the following are planned:

1. All adverse events recorded between screening and first dose of study medication.
2. All treatment emergent adverse events.
3. All emergent and related adverse events.
4. All treatment emergent hepatic adverse events.
5. All treatment emergent hematologic adverse events.
6. All adverse events that caused permanent discontinuation of study drug.
7. All adverse events that caused temporary interruption of study drug.
8. All serious adverse events and.
9. All serious and related adverse events.

Annual safety analysis will be reported to DSMB.

Laboratory abnormalities.

Laboratory results will be presented as both actual value as well as a function of normal range. Selected data (using conventional units) will be summarized by the change from baseline in laboratory test. If baseline data are missing, then any graded abnormality is considered treatment emergent.

Interim analysis.

A Preliminary Study of the Efficacy and Safety of Carbamazepine in Severe Liver Disease Due to Alpha-1 Antitrypsin Deficiency

Interim analysis of safety data will be performed after all subjects have completed 24 weeks of therapy. Interim analysis of adverse events will be made quarterly throughout the study.

Additional analyses will be performed at the request of the DSMB, if there are any concerns raised by adverse events or serious adverse events reported.

EFFORTS TO ENSURE ADHERENCE TO THE PROTOCOL

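### Treatment emergence is defined by start date alone, so an adverse event that begins between consent and first dose and worsens on study drug can drop out of the treatment-emergent summaries

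*Combined protocol and SAP*

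**What the plan says.** Under Safety analysis, the adverse events paragraph gives one rule for dating: "Events will be summarized based on the date of onset for the event". The next sentence says that a treatment-emergent event is "defined as an adverse event that begins on or after the date of first dose of study drug". It is followed by: "Events that occur prior to the first dose of study medication or after the last dose of study medication will be summarized separately". The first of the nine planned summaries is "All adverse events recorded between screening and first dose of study medication". Summaries 2 to 5 cover treatment-emergent events: all of them, those judged related, hepatic events and hematologic events. Summaries 6 to 9 cover events that led to permanent discontinuation or temporary interruption, serious events, and serious related events. None of these four is restricted to treatment-emergent events.

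Three other places bear on the point.

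- The Definition paragraph under Adverse events describes an adverse event as "any adverse change from the patient's baseline (pre-treatment) condition, including intercurrent illness which occurs during the course of the trial", counted once consent is signed.
- The section on data collection procedures for adverse events says "Patients will be followed for all ongoing unresolved adverse events until they are either resolved", or until the patient is judged stable.
- The section on screening and management for specific adverse events says that "changes in laboratory values after initiation of the study drug will need to be assessed within the context of the patient's baseline laboratory tests". It also says that a minimum size of change will decide when a laboratory change counts as an adverse event, and it names CTCAE version 4.0 as the grading system.

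No section says whether an event that began before first dose and becomes more severe on drug gets a new record with a new onset date or keeps the one it has.

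**The concern.** A definition of treatment emergence usually has two parts: events that are new after first dose, and events that were present before and got worse after it. This plan has only the first part. Because the onset date alone decides the table, a complication that starts in the screening period and becomes more severe on study drug can be reported as if treatment had no part in it.

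Safety and tolerability is Objective 4. The section on use of the drug in liver disease states that clinical studies in such patients are lacking, so the treatment-emergent hepatic and hematologic tables are among the more informative outputs of the trial. If on-drug worsening is left out of them, they understate harm. If the drug causes some of that worsening, the difference between the arms is understated as well.

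**Working it through.** The plan has no figure to reproduce. The check is to set the passages side by side and follow three kinds of event through them.

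**Is there a pre-dose window in which an event can arise?** Yes. Collection begins at consent, and summary 1 is reserved for the period from screening to first dose. In that period the protocol places blood tests, AT phenotyping, HLA typing, a Doppler sonogram, and a sedated transvenous pressure measurement with biopsy. Some subjects also receive plasma or platelets. Under Overall patient management, drugs that affect the pressure reading are stopped for 3 days beforehand. The Treatment Trial section allows enrolment and first dose on the same day once eligibility is verified. That shortens the step from eligibility to dosing, but does not make consent to first dose a single day. The documents do not state the length of the interval.

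**Three cases.**

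| Case | Event | Reading | Where it is reported |
|---|---|---|---|
| (a) | Condition present before consent (e.g. treated ascites), worse on drug | An adverse change from the pre-treatment condition, starting on drug | Treatment emergent: no gap |
| (b) | Event begins between consent and first dose, worse on drug; worsening entered as a new event | Onset is the date of worsening | Treatment emergent: no gap |
| (c) | Same event as (b), kept as one record | Onset is before first dose | Summary 1 only; absent from summaries 2 to 5 |

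**Do the documents choose between (b) and (c)?** No. The definition refers to the baseline, pre-treatment condition but does not say when that condition is fixed. If it is the state at first dose, later worsening is a fresh adverse change and (b) follows. If it is the state at consent or screening, the worsening continues a change already recorded, and the onset rule leads to (c). The follow-up sentence sets how long patients are followed and says nothing about splitting records. Two coders could therefore place the same subject in different tables.

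**Would case (c) appear elsewhere?** Only in part.

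- Serious events (summaries 8 and 9): the Definition paragraph lists worsening ascites, variceal bleeding, worsening hypersplenism and hepatic encephalopathy among disease outcomes that are not treated as serious. It concedes that hypersplenism is difficult to tell from marrow toxicity.
- Discontinuation and interruption (summaries 6 and 7): the dose alteration section provides for 50% reductions for low counts, raised ALT and prolonged INR. A reduction is neither a discontinuation nor an interruption, and no summary is planned for events that lead only to one.
- Laboratory summaries: these report change from baseline for selected tests, plus values at end of therapy and at the largest deviation from normal. They would show a falling count or sodium, but not ascites or encephalopathy as events.

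**Leverage of one subject.** The planned arms are 20 on carbamazepine and 10 on placebo. One misfiled subject changes an arm's proportion with an event by 1/20 = 0.05, or 5 percentage points, on carbamazepine, and by 1/10 = 0.10, or 10 percentage points, on placebo, provided that the subject has no other event in the same table.

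**The case against.** The strongest reply is that the adverse event definition already does the work. It measures change against the patient's pre-treatment condition, so a problem that is ongoing at first dose is part of that condition and any worsening afterwards is a new event that starts on drug. On-drug laboratory changes are likewise judged against the patient's own baseline. Child-Pugh and MELD scores are calculated at each visit, discontinuations and interruptions are tabulated whatever the onset date, the rule applies equally to both blinded arms, and the safety analysis is descriptive.

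Much of this stands. A reader might infer that the rule loses worsening of the ascites, varices and hypersplenism with which subjects enter. The documents do not support that: these are baseline conditions and fall under case (a). A reader might also infer that a screening-period event that worsens is certain to be filed as pre-dose, or that the plan requires an ongoing event to be kept as a single record. Neither is stated. The laboratory rule also weakens the concern for events defined by a laboratory value.

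What does not stand is that the gap is closed. The definition can be read to produce case (b), but the Safety analysis section gives an explicit onset rule with no worsening clause, and that is the rule a programmer will apply. The other outputs miss or blur the hepatic and hematologic worsening that summaries 4 and 5 are meant to show. Equal application to both arms does not protect the comparison if the drug itself makes worsening more frequent.

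**Conclusion.** The concern holds in a limited form. An adverse event that begins between consent and first dose and worsens on study drug can be reported as pre-dose and omitted from summaries 2 to 5, because the definition has no worsening clause and the documents do not say how the worsening is dated. The gap does not extend to conditions already present at entry.

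Its size cannot be given as a count of subjects. That would need the rate of screening-period events, the share that worsen on drug, and the share kept as one record, and the documents supply none of the three. What can be said is the effect per misfiled subject: 5 percentage points on carbamazepine and 10 on placebo, assuming the planned 20 and 10 are all analysed and the subject has no other qualifying event. The efficacy analyses, power and type I error are unaffected. It is worth correcting because the tables concerned serve a stated objective and the correction is small.

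**What to change.** In the adverse events paragraph under Safety analysis, define a treatment-emergent event as one that begins on or after first dose, or that worsens in CTCAE grade on or after first dose compared with its highest pre-dose grade. State that the date of worsening is taken as the onset of the treatment-emergent event, in line with the adverse event definition, and apply this to summaries 2 to 5. The event as first recorded can stay in summary 1 at its pre-dose grade.

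The cost is a grade-change date on the adverse event form and slightly more events counted in both arms. CTCAE version 4.0 grading is already planned, so no new scale is needed, and no treatment rule changes.

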During therapy, study subjects will be seen on a regular basis to assess their clinical status and to obtain standard biochemical measures of liver and renal function, cell counts, etc. Visits will also include a full history and physical examination. Specific assessments and queries will be made for any signs or symptoms of liver disease. Child-Pugh (CP) score and MELD score will be calculated at each study visit. Other than blood collection during study visits, no additional invasive testing is proposed until the week 52b visit when a repeat liver biopsy and HVPg will be obtained. The procedure for the liver biopsy and HVPg will be identical to the procedure used in the screening visit. Data will be collected from procedures undertaken as part of clinical follow up (e.g. endoscopy reports, imaging studies, etc.).

If the study subject undergoes liver transplantation during the study period, samples will be obtained at the time of surgery to provide follow up data. If a subject dies during the study period and the family consents to an autopsy, samples of liver tissue will be obtained at autopsy to provide follow up data. In these cases, follow up HVPg measurements will not be available.

Potential for suicide attempts will be monitored with the Columbia Suicide Severity Rating Scale (C-SSRS) at study visits the week of enrollment through week 52a. It is a semi-structured, clinician-administered instrument to track severity of both suicidal behavior and ideation. This measure is reliable and valid and has been used in previous clinical trials (44, 45). Patients will be withdrawn from the trial if the C-SSRS identifies suicidal ideation or behavior and then the patient will then be referred for mental health evaluation and treatment.

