2. WBC <1,000
 - a. Decrease dose by 50%
3. Neutrophil count <500
 - a. Decrease dose by 50%
4. Platelets < 20,000
 - a. Decrease dose by 50%
5. ALT > 500 IU/dl
 - a. Decrease dose by 50%
6. INR \geq 1.8 not corrected by 5 mg of vitamin K
 - a. Decrease dose by 50%

Guidelines for subsequent Study drug dose adjustments

Indications to discontinue CBZ

1. Child-Pugh score > 12
2. Hepatic encephalopathy uncontrolled with outpatient medical therapy
3. Total bilirubin > 7 mg/dL
4. Evidence of anticonvulsant hypersensitivity syndrome
 - a. Fever > 38.5 and
 - b. Lymphadenopathy, and
 - c. Erythematous, maculopapular, pruritic, or exfoliating rash
5. WBC <1,000 despite 2 weeks of Carbamazepine dose reduction, may resume therapy at 50% of starting dose when WBC > 3,000
6. Neutrophil count <500 despite 2 weeks of Carbamazepine dose reduction, may resume therapy at 50% of starting dose when ANC > 1,500
7. Platelet count <20,000 despite 2 weeks of Carbamazepine dose reduction, may resume therapy at 50% of starting dose when plt > 40,000
8. Hgb <8.5 mg/dl
9. INR \geq 2.5 not corrected by 5 mg of Vitamin K

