A Preliminary Study of the Efficacy and Safety of Carbamazepine in Severe Liver Disease Due to Alpha-1 Antitrypsin Deficiency

4. Evidence of anticonvulsant hypersensitivity syndrome.
5. Leukocyte count <1,000 despite 2 weeks of CBZ dose reduction.
6. Neutrophil count <500 despite 2 weeks of CBZ dose reduction.
7. Platelet count <20,000 despite 2 weeks of CBZ dose reduction.
8. Hemoglobin <8.5 mg/dl.
9. INR greater than or equal to 2.5 not corrected by vitamin K 5 mg.
10. ALT >750 IU/L.
11. Pregnancy.
12. Breast feeding.
13. Evidence for behavior or ideation predisposing to suicide or increase in C-SSRS score of 1 from previous test score.
14. Persistent non-adherence to medication study regimen.

DATA RETRIEVAL AND STORAGE

A data repository in the University of Pittsburgh computing facility has been established to accept all information about subjects including; demographics, history, physical exam, labs and a tracking/event file. The tracking/event file is designed for important events: study entry; study completion; adverse events; treatment failures; exits; dropouts; protocol violations; etc. Security of the deposited data will be maintained through the use of unique patient identifier numbers and passwords to enter the repository. Data can be exported from the repository for reporting and statistical analysis.

Data quality and accuracy will be audited annually by comparing what is in the database with the medical records of the patients.

The electronic data storage and retrieval system used for the purpose of this clinical investigation has not been fully validated for compliance with the FDA regulations at 21 CFR Part 11 taking into account the limited size and scope of the investigation.

DATA AND SAFETY MONITORING PLAN

The Data and Safety Monitoring Board (DSMB) will consist of individuals who are independent of the institutions and investigators participating in the CBZ study, and who have no financial ties to the outcome of the trial. The ongoing review of the data by this independent committee assures the investigators and the study sponsor that the trial can continue without jeopardizing patient safety. Individuals on the DSMB will be responsible for monitoring data and safety during the course of this study.

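### Hemoglobin below 8.5 and ALT above 750 stop treatment, but neither has an entry limit, so a subject already past either stop can be randomized

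*Combined protocol and SAP*

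**What the plan says.** **Stops.** Indications to discontinue CBZ and the Complete list of withdrawal criteria both name hemoglobin and ALT. The withdrawal list has "Hemoglobin <8.5 mg/dl" and ALT above 750 IU/L, and the discontinuation list uses the same two values. Both are absolute values, and neither requires a dose reduction first.

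**Entry.** The exclusions for the screening assessment and for the Treatment Trial set numeric limits for Child-Pugh score, bilirubin, INR, creatinine, WBC and platelets. The Summary repeats these. None of the three gives a hemoglobin or ALT value.

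**Expected baseline.** Screening and Management for Specific Adverse Events expects entering subjects to have raised ALT and to be "below the normal range for hemoglobin, WBC, platelets and neutrophils count". It does not say how far.

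**Restart.** Under Indications to discontinue CBZ, the ALT stop carries "May resume previous dose when ALT < 500". The WBC stop carries "may resume therapy at 50% of starting dose when WBC > 3,000", and neutrophils and platelets have parallel rules. The withdrawal list gives the same events without a restart rule, for example "Leukocyte count <1,000 despite 2 weeks of CBZ dose reduction".

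**C-SSRS.** On-treatment assessments says "Patients will be withdrawn from the trial if the C-SSRS identifies suicidal ideation or behavior". The discontinuation list defines the evidence as an "increase in C-SSRS score of 1 from previous test score". The withdrawal list has "Evidence for behavior or ideation predisposing to suicide or increase in C-SSRS score of 1 from previous test score".

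**The concern.** A stop criterion marks a state in which the plan considers it unsafe to keep dosing. Where a measure has a stop but no entry limit, a subject can start treatment in that state. The plan guards against this for its other numeric liver and blood-count limits, so the omission for hemoglobin and ALT looks like an oversight.

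ALT matters for this drug: the Safety section of the background reports raised transaminases in 5-10% of people treated with CBZ. The Treatment Trial section allows enrollment and first dose on the same day. Efforts to Ensure Adherence to the Protocol counts enrolling every eligible patient and starting CBZ promptly as part of adherence. Both push toward treating a subject who meets the written criteria. What is at stake is the safety of an individual subject, not the efficacy comparison.

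**Working it through.** No power or alpha figure is involved. The check sets entry limits beside stops. Entry limits come from the Treatment Trial exclusion criteria, which match the screening exclusions on these items. Stops come from Indications to discontinue CBZ and the Complete list of withdrawal criteria.

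| Measure | Excluded at entry | Stopped on treatment | Gap |
|---|---|---|---|
| Child-Pugh | 12 or more (highest allowed 11) | above 12 (lowest that stops 13) | 13 - 11 = 2 points |
| Bilirubin, mg/dl | above 5 | above 7 | 7 - 5 = 2 |
| INR | above 2.2 | 2.5 or more, uncorrected by vitamin K | 2.5 - 2.2 = 0.3 |
| WBC | below 1,500 | below 1,000 despite 2 weeks at reduced dose | 1,500 - 1,000 = 500 |
| Platelets | below 25,000 | below 20,000 despite 2 weeks at reduced dose | 25,000 - 20,000 = 5,000 |
| Hemoglobin | no limit | below 8.5 | none guaranteed |
| ALT, IU/L | no limit | above 750 | none guaranteed |

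Uncontrolled encephalopathy, pregnancy and breast feeding are also barred at entry as well as being stops. The neutrophil stop (below 500) has no entry limit of its own, but it requires two weeks of dose reduction first, so it cannot be met at entry.

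Two worked cases, each assuming all other criteria are met:

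- Hemoglobin 8.0 g/dl at screening: no exclusion applies, and 8.0 < 8.5, so the stop is met before the first dose.
- ALT 800 IU/L at screening: no exclusion applies, and 800 > 750, so the stop is met before the first dose.

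The first scheduled on-treatment visit is week 4. Dosing starts at 400 mg/day and rises by 200 mg/day each week. After three increases it is 400 + 3 × 200 = 1,000 mg/day, and after four it is 400 + 4 × 200 = 1,200 mg/day, the adult maximum. A subject who entered past a stop could therefore be near full dose by that visit. Alterations in liver function promises more frequent tests in the first four months, and the flow chart is not in the supplied text, so it cannot be said that no earlier blood test is scheduled.

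Unit: hemoglobin is printed in mg/dl in both lists. It is taken as g/dl, because a literal reading would make the stop impossible to meet.

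**The case against.** **Safeguards at entry.** The investigators see the screening bloods and may add safety visits. One exclusion removes other causes of active liver disease and could catch some subjects with very high ALT. Another removes past bone marrow depression and could catch some with low hemoglobin. On treatment, ALT above 500 triggers a halved dose. All of this lowers the risk, and nothing in the documents suggests such subjects are common. But none of these rules sets a hemoglobin or ALT value at entry. The bone marrow exclusion sets aside hypersplenism and would not reach anemia from variceal bleeding. The advice to judge laboratory changes against baseline concerns what counts as an adverse event; it does not alter the listed stops.

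**A tempting stronger reading: the ALT and blood-count stops contradict each other**, being a hold in one list and a withdrawal in the other. The documents do not establish that. The cut-offs are identical. The withdrawal list does not mention restart, but it does not forbid it. Screening and Management for Specific Adverse Events reserves its bar on restarting for Child-Pugh, encephalopathy and bilirubin. Adverse Events and Toxicity Management gives rules for resuming after a temporary hold, and Safety analysis tabulates temporary interruption apart from permanent discontinuation. The specific restart rules can therefore govern. What remains is unclear wording: one event sits under a restart rule and also in a list headed as withdrawal.

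**A second stronger reading: suicidal ideation with a PHQ-9 below 10 and no past attempt goes undetected.** That is not supported either. The C-SSRS is given from the week of enrollment, and any ideation it identifies leads to withdrawal. What remains is a difference in trigger. Read alone, the discontinuation list would not stop a subject with stable ideation, while the other two places would. Applying the strictest rule satisfies all three.

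**Conclusion.** The entry gap holds on the text. Hemoglobin below 8.5 g/dl and ALT above 750 IU/L are stops with no matching entry limit, so a subject already past either can be randomized and dosed without breaking any written criterion. How often this would happen is unknown, and the documents do not suggest it is common. No effect on power or the primary analysis is claimed.

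This is a modest, inexpensive safety improvement. It assumes that the hemoglobin unit is meant as g/dl and that no entry limit appears only in the flow chart, which is not in the supplied text. The restart and C-SSRS points are secondary matters of wording and do not show contradictory rules.

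**What to change.** **Main change.** Add to the Treatment Trial exclusion criteria, and repeat in the Summary: hemoglobin below 8.5 g/dl or ALT above 750 IU/L on the latest screening laboratory values. This ensures only that nobody starts past a stop. Whether to set stricter limits, leaving a margin as for bilirubin or INR, is for the sponsor's clinicians. Correct the hemoglobin unit in both stop lists.

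**Wording alignment.** In the Complete list of withdrawal criteria, state that the ALT, WBC, neutrophil and platelet stops follow the restart rules under Indications to discontinue CBZ. In that discontinuation list, use the same C-SSRS trigger as the other two places: any ideation or behavior, or a one-point rise.

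**Cost.** Protocol wording only. Screening bloods are already drawn for liver function, and the WBC and platelet limits already require a blood count. The downside is possibly a few more screen failures in a rare disease.
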